Only the collaborating investigators and data coordinator located at each the Advocate and Health Care Partners sites will have the key linking survey data to names of their own patients completing the survey.

Potential Risks

As described above, there are no physical, financial, or legal risks to patients selected for participation in this project. The principal risks from this study concern the potential for loss of confidentiality.

Adequacy of Protection Against Risks

Recruitment and Informed Consent

Informed consent will be obtained from all selected patients before completion of the survey. As described above, a written consent letter will be included with the mailed surveys and phone consent will be specifically obtained at the beginning of each follow-up CATI interview.

Protections Against Risk

All information with the potential to identify study participants will remain housed at Advocate Health and Health Care Partners, respectively, only accessible to Advocate Health and HealthCare Partners staff.

Potential Benefits of the Proposed Research to Human Subjects and Others

Please see above under Protection of Human Subjects – UC Berkeley.

Importance of the Knowledge to be Gained

Please see above under Protection of Human Subjects – UC Berkeley.

INCLUSION OF WOMEN AND MINORITIES

Please see the detailed enrollment table above under Protection of Human Subjects – UC Berkeley.

INCLUSION OF CHILDREN

Individuals under 18 will be excluded from the proposed research as the chronic adult conditions proposed for study for this project are not relevant to children.

REFERENCES CITED

2. Muhlestein D. Continued growth of public and private accountable care organizations. *Health Affairs blog*. 2013.
3. Kish L. The Blockbuster Drug of the Century: An Engaged Patient. 2012 [updated 28 Aug; cited 2013 12 Dec]; Available from: <http://www.hl7standards.com/blog/2012/08/28/drug-of-the-century/>.
4. [name] S, Wu F, Colla C, Fisher ES, Lewis VA. Mapping the Unicorn: A Taxonomy of Accountable Care Organizations. 2014;Submitted.
5. [name] S, McClellan SR, Ramsay P, Casalino L, Ryan A, Copeland K. Physician practice participation in accountable care organizations: the emergence of the unicorn *Submitted*. 2014.

HealthCare Partners ACO was formed in 2010 as one of the early Dartmouth-Brookings demonstration ACOs⁴⁶. They hold both CMS and private payer risk-based contracts collectively accountable for 50,000 lives. They serve high proportions of Medicaid patients in low-income communities who tend to face many social and financial barriers to self-management of diabetes and CVD. Approximately 55% of HCP's Southern California patients are Latino. HCP and the HCP Institute for Applied Research and Education have extensive expertise leading patient-centered HIT development and research projects. For the past 3 years, the HCP Institute through earned, competitive grant funding, has been refining the application of remote patient monitoring of chronic disease in older adult patients using interactive voice response technology (IVR). Based on a third-party evaluation by the Center for Connected Health at Partners Healthcare in Boston, HCP's IVR system resulted in significant improvements in appropriate care⁸⁶. HCP's implementation of patient-centered HIT, particularly focused on integrating informal caregivers⁸⁷, are important patient activation and engagement innovations to study in the context of improving patient-reported outcomes, as there is considerable variation in the use of patient-centered HIT across HCP's practices. They are highly committed to this study as indicated by their letter of support and related materials in this proposal.

PRINCIPAL INVESTIGATOR (LAST, FIRST, MIDDLE): [name]

Both Advocate and HealthCare Partners will subcontract with UC Berkeley to perform the following tasks:

Securely transmit names, addresses, and contact information for 273 adult patients with diabetes and/or cardiovascular disease with at least 2 visits in the baseline year (2013) from each of eight primary care practices affiliated with our Accountable Care Organization (ACO) to the patient survey vendor selected for the project.

Securely transmit a de-identified patient-level data to the UC Berkeley research team in Months 7 and 19 covering 2013 and 2014 period, respectively. These datasets will include adult patients with diabetes and cardiovascular disease with at least 2 visits in the baseline year (2014) and the data elements include select sociodemographic information and clinical care process and outcome data using Healthcare Effectiveness Data Information Set (HEDIS) definitions for measures of chronic illness care.

Provide the UC Berkeley research team with the names, emails, and mail contact information for all primary care clinicians and staff of the eight practices so that a survey of team culture, leadership, relational coordination, and perceived team effectiveness can be conducted at two points in time (at baseline, between months 0-6, and again between months 13-18). The data manager at each ACO will facilitate the completion of the surveys by coordinating implementation with practice managers and ensure that participants have time during work hours to complete the survey.

Provide feedback to the UC Berkeley team on the individual practice feedback reports that will include key comparisons from the patient and clinician/staff surveys. These reports will be shared with primary care clinicians, staff, and patient advisory group members after each data collection period.

Work with the Berkeley team to coordinate two site visits lasting two to three days for the research team to interview key people, some patients, and to observe meetings. The purpose of these visits is to learn more about the successes and challenges of delivering more patient-activated and engaged care and to help the research team better understand the quantitative data being collected.

Assist with recruiting six patient representatives from the target population to serve on an advisory board that will review study instruments and provide recommendations and feedback for the ACO practices to consider as they refine and improve their PA&E efforts. The ACOs will provide institutional support to the patient advisory board and will provide patient advisors with project stipend support for their participation each year.

PRINCIPAL INVESTIGATOR (LAST, FIRST, MIDDLE): [name]

APPENDIX (Optional)

(Use continuation pages as needed. You may provide an appendix of up to 10 pages to include additional materials that you think may be useful to describe, e.g., survey instruments, interview guides, etc. Note, however, that reviewers are not required to include the appendix when they review and assess your application.)

Appendix I. Patient Activation and Engagement Site Assessment Survey

For most items below, the response categories will be:

Yes, fully implemented	Yes, partially implemented	Yes, but not regularly implemented	No
------------------------	----------------------------	------------------------------------	----

Begin survey:

Please indicate the extent to which your practice site uses the following patient activation and engagement strategies for patients with diabetes and/or CVD.

A. Patient care outreach in regard to disease prevention and health promotion

1. Conducts a Health Risk Assessment (HRA) Survey
2. Feedback to patients on results of their HRA
3. Ongoing monitoring of HRA results (assess over time changes)
4. Refer patients to a disease prevention or health promotion program as a result of the HRA
5. Sponsor or participate in a community-based Healthy Eating Program
6. Sponsor or participate in a Community-based Physical Activity Program
7. Sponsor or participate in a Farmers Market
8. Have a Employee Health Promotion/Prevention/Wellness program
9. Sponsor or participate in School Health Clinic interventions

B. Changes in the clinician-patient relationship, particularly in the areas of communication, motivational interviewing, and involvement in treatment care plans.

10. HRA results available electronically to care team members (through EHR registry) at the point of care
11. Clinicians are trained in motivational interviewing techniques
12. Clinicians consistently use motivational interviewing techniques in communicating with patients, e.g. encourage patients to ask questions
13. Clinicians consistently encourage patients to discuss their work, home life, and social situation
14. Staff note patient preferences for treatment in the patient's record
15. Staff are trained in motivational interviewing techniques
16. Staff consistently use motivational interviewing techniques in communication with patients, e.g., encourage patients to ask questions
17. Select staff serve as "health coaches" for patients seeking to modify their lifestyle
18. Patients can routinely provide information on their care and their health via a patient portal (not just access)
19. Telehealth is consistently made available to patients with diabetes

PRINCIPAL INVESTIGATOR (LAST, FIRST, MIDDLE): [name]

20. Telehealth is consistently made available to patients with cardiovascular disease

C. Shared decision-making

21. Clinicians consistently involve patients in developing treatment goals
22. Goal-setting for behavioral changes with patients as a result of their HRA
23. Provide eligible patients with shared decision making videos
24. Physicians consistently have follow up discussions with patients regarding their treatment options and preferences
25. There is a formal evaluation of the impact of shared decision making on patient care choices, outcomes of care, and patient experience with their care
26. There exists an organized follow up program to assist patients in managing their medications at home, e.g., pharmacist-led medication management
27. Shared medical appointment (group visits) are available for patients with diabetes
28. Shared medical appointment (group visits) are available for patients with cardiovascular disease
29. Peer to Peer (Patient to Patient) programs are available for patients with diabetes
30. Peer to Peer (Patient to Patient) programs are available for patients with cardiovascular disease
31. Programs to improve family participation and support for patients with diabetes
32. Programs to improve family participation and support for patients with cardiovascular disease

D. Patient self-management of their condition

33. At home monitoring devices and/or tools to assess medication management, blood pressure, blood sugar, and lipids are made available to patients

E. End of life/advanced serious illness care patient engagement and family involvement

34. Clinicians consistently discuss the importance of patient advanced directives (Care for Older/Vulnerable Adults)
35. Clinicians consistently discuss hospice care options with patients (Care for Older/Vulnerable Adults)
36. Clinicians consistently discuss the availability of both hospital based and community based palliative care with patients (Care for Older/Vulnerable Adults)

F. Patient involvement in the overall design of care and in organization-wide efforts to improve the quality of care

37. Patient advisory councils exist for patients with diabetes
38. Patient advisory councils exist for patients with cardiovascular disease
39. Patients consistently participate in quality improvement teams
40. Patients are involved in helping to govern the clinic/practice

Appendix II. Patient Activation, Self-Reported Outcomes of Care, and Patient Experience
 (Number of questions = 65)

Measure	Item Count	Example Content	Internal Consistency Reliability	Why Selected (Why alternatives were not?)
Patient Activation Measure (PAM-13)	13	
 • When all is said and done, I am the person who is responsible for taking care of my health • I know how to prevent problems with my health • I am confident that I can follow through on medical treatments I may need to do at home. 	0.90+	PAM is a widely used measure that has high internal consistency, has been shown to be associated with a range of patient-reported outcomes, and is also useful to guide the quality improvement activities of participating ACO practices ¹⁰ .
Patient Assessment of Chronic Illness Care (PACIC-11)	11	
Over the past 6 months, when I received care for my chronic conditions. How often was I:
 
 • Given choices about treatment to think about • Helped to set specific goals to improve my eating or exercise. • Helped to plan ahead so I could take care of my condition even in hard times. 	0.93	There are few validated measures of patients' experiences of chronic illness care. We considered using two alternate measures- the Ambulatory Care Experiences (ACES) quality of chronic illness care composite ⁸⁸ and the recently developed Integrated Patient Care measures ⁸⁹ (Singer et. al). The PACIC was preferred because of it has more extensive research highlighting the reliability and utility of the measure. PACIC was also preferred because validation studies have been conducted with the brief measure (PACIC-11) and is sensitive to change over time. ⁵⁸
Patients' Experiences of Primary Care Teams (Ambulatory Care Experiences Survey)	5	
Screener: Are there nurses or other providers in your personal doctor's office who play an important role in your care?
 
 • In the last 6 months, how often did these nurses and other providers in your personal doctor's office explain things in a way that is easy to understand? 	0.70	Few validated measures of patients' experiences of primary care teams exist. The "care team" composite measure of the Ambulatory Care Experiences Survey (ACES) survey has been previously used in peer-reviewed research and has acceptable internal consistency reliability. The recently developed Integrated Patient Care measures ⁸⁹ includes 2

PRINCIPAL INVESTIGATOR (LAST, FIRST, MIDDLE): [name]

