Patient Reported Outcome Measure – PACIC-11

The Patient Assessment of Chronic Illness Care scale (PACIC-11) developed and validated by Glasgow et al⁵⁸ (Medical Care, 2005; see Appendix II) will be used to assess the extent to which practices engaging in more PA&E activities and with higher team functioning will be able to effectively improve patients' experiences of chronic illness care over time. The PACIC-11 has high Cronbach's alpha internal consistency, reliability of 0.93, and reasonable test-retest reliability of 0.58. It also demonstrates convergent validity with the Hibbard PAM measure and several dimensions of the Ambulatory Care Experiences Survey (ACES), the precursor to the Clinician Group Consumer Assessment of Healthcare Providers and Systems (CG-CAHPS) survey ([name] and Crane 2011)⁵⁹. We will supplement the PACIC-11 with selected items from the Ambulatory Care Experiences Survey (ACES) focused on patients' experiences of primary care teams ([name], Rogers et al., 2007)⁶⁰. (See Appendix II)

Clinical Measures

Based on each site's EHR, we will have de-identified data for blood pressure, lipids, and HbA1c to measure percentage of hypertensive patients with blood pressure controlled (<140/90 mm Hg), percentage of patients with diabetes with blood sugar controlled (HbA1c <8.0%), and percentage of patients with cardiovascular conditions or diabetes whose lipids are controlled (LDL-C <100 mg/dL). The patient survey sampling frame includes "established" patients of each primary care physician and team. The adult diabetic and CVD patients will need to have at least two primary care visits in the baseline year (2013) to improve the reliability of reports of patients' experiences of care and to focus on an established patient population that has a high propensity to maintain clinical relationships and receive routine primary care over time. Since attribution of patients to practices and PCPs is a contentious issue in performance measurement in improvement^{61, 62}, restricting the sample to patients with diabetes and/or CVD who have ongoing relationships will also aid in team acceptance of the feedback data.

Patient Demographics

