Appendix II. Patient Activation, Self-Reported Outcomes of Care, and Patient Experience
 (Number of questions = 65)

Measure	Item Count	Example Content	Internal Consistency Reliability	Why Selected (Why alternatives were not?)
		
 How would you rate the coordination of your care between these nurses and other providers and your doctor? Thinking about these nurses or other providers in your doctor's office, how would you rate their knowledge of you as a person, including values and beliefs that are important to you? 		items related to care team coordination and these questions have similar content as the ACES items ([name], et al, 2007). ⁹⁰
Ability to Participate in Social Roles and Activities (PROMIS Short Form 8a)	8	
 I have trouble doing all of the family activities that I want to do I have to limit my regular activities with friends. I have trouble doing all of the work that is really important to me (include work and home) 	0.85-0.94	The PROMIS social role subscale was selected because the composite covers a health domain central to patient activation and engagement. Further, the measure was developed through extensive item preparation and review, EFA-, CFA- and IRT-guided item banks help provide increased measurement precision and flexibility. ⁹¹
Patient Health Questionnaire (PHQ-4) Depression and Anxiety	4	
Over the past 2 weeks, how often have you been bothered by these problems:
 
 Feeling nervous, anxious or on edge Not being able to stop or control worrying Feeling down, depressed, or hopeless Little interest or pleasure in doing things 	0.82	Compared to the PROMIS measures of anxiety and depression, the PHQ-4 is parsimonious, is used more extensively in primary care settings for quality improvement and research purposes. While the PROMIS measures are longer and cover a broader range of symptoms, research has not demonstrated the relative advantage of the PROMIS measures compared to the PHQ-9 or PHQ-4 for use in primary care settings. ⁹²

PRINCIPAL INVESTIGATOR (LAST, FIRST, MIDDLE): [name]

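### The supplementary ACES care-team score can be computed only for patients who report a care team, an answer that PA&E may itself change, so high and low practices may be compared on differently selected patients

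*Combined protocol and SAP*

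**What the plan says.** The Measures section, under PACIC-11, gives ACES a secondary place: "We will supplement the PACIC-11 with selected items from the Ambulatory Care Experiences Survey (ACES) focused on patients' experiences of primary care teams". Appendix II lists the care-team measure with five items. It starts from a gate, a question that begins "Screener: Are there nurses or other providers in your personal" and asks whether such staff matter to the patient's care. The example items that follow refer back to the people named there, for instance one on clarity of explanation, which begins "In the last 6 months, how often did these nurses and other providers in your personal doctor's office explain things in a way that", and one on coordination, "How would you rate the coordination of your care between these nurses and other providers and your doctor".

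The exposure is the overall score on the 40-item checklist in Appendix I, with practices drawn from the top and bottom quartiles in each ACO. Item 15 scores staff training in motivational interviewing and item 16 its use: "Staff consistently use motivational interviewing techniques in communication with patients". Item 17 covers staff who act as health coaches. Item 26 covers organised help with medicines at home, such as a pharmacist-led programme. The section on teamwork assessment instruments also links better activation and engagement to new roles for staff who are not physicians.

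The Aim 1 model regresses patient experience (PE) on high/low PA&E, PAM, practice size and casemix. The casemix factors named are age, sex, education and comorbidity. The Aim 4 model regresses the change in PE on the changes in PA&E and PAM. Nothing states how a patient who answers no is scored, or how one who passes at only one wave enters the change analysis.

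**The concern.** If only those who answer yes have a score, the ACES contrast is made within a subgroup defined after exposure. PA&E work that gives nurses, coaches or pharmacists a larger role could lead more patients to answer yes. The scored patients in high practices would then include people who, in a low practice, would have had no score. A difference between groups could come from who is scored and not from how well the team works. Equally, a real benefit could be hidden.

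The listed casemix factors do not measure contact with staff, and a multilevel model deals with clustering, not with this selection. The change analysis has the same weakness in a sharper form. A patient who gains or loses an engaged team between waves has no change score, although that shift is something PA&E might be expected to produce. Wave 1 results are fed back to practices between the two surveys (Table 3), so the pass rate could itself move.

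**Working it through.** **1. The plan's own survey yield.** Inputs (study design and patient selection sections): 16 practices, 273 patients each, 3% undeliverable, 50% and 65% response, 20% attrition.

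- 16 x 273 = 4,368
- 4,368 x 0.97 x 0.50 x 0.65 x 0.80 = 1,101.6, or 68.9 per practice

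This agrees with the stated 1102 and 69. It counts all two-wave respondents. The plan gives no separate number for patients with an ACES score.

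**2. Scored patients at an assumed pass rate.** With 60% passing, 68.9 x 0.60 = 41.3 two-wave patients per practice have a score if the same patients pass both times. If passing were independent between waves, 68.9 x 0.60 x 0.60 = 24.8 would. The 60% is an assumption.

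**3. Possible bias when true care-team experience is equal.** Let pH and pL be the pass rates in high and low practices. Suppose a share pL would pass in either setting with mean score M, and high practices add a further share pH - pL whose mean is M - g. Then:

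- mean among scored patients, low: M
- mean among scored patients, high: M - g x (pH - pL)/pH
- spurious high-minus-low difference: -g x (pH - pL)/pH

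All pass rates and gaps below are assumptions:

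| pH v pL | (pH - pL)/pH | g = 0.3 SD | g = 0.8 SD |
|---|---|---|---|
| 60% v 50% | 0.167 | -0.05 | -0.13 |
| 70% v 50% | 0.286 | -0.09 | -0.23 |
| 80% v 50% | 0.375 | -0.11 | -0.30 |

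The result is zero if pH = pL or g = 0. It turns positive if the extra passers score higher (g negative).

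**4. A second model.** Assume a normal latent variable that governs passing and has correlation r with experience. The shift is r x [L(pH) - L(pL)], where L(p) is the standard normal density at the p-quantile divided by p. For 70% v 50% and r from 0.2 to 0.5 this gives -0.06 to -0.15 SD. For 80% v 40% it gives -0.12 to -0.31 SD. With r = 0 it is zero. The order of magnitude is similar, but the inputs are again assumed.

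**5. Why practice-mean imputation is no remedy.** If a practice has pass rate p and scored mean m, giving its screened-out patients the value m returns p x m + (1 - p) x m = m. The unadjusted practice mean is unchanged and only the apparent sample size grows. If screened-out patients are instead given m + d, the high-minus-low difference changes by (1 - pH) x d - (1 - pL) x d = -(pH - pL) x d. At 70% v 50%, d = -0.8 SD moves it by +0.16 SD and d = +0.8 SD by -0.16 SD.

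**The case against.** The strongest reply is that this is a detail of a supplementary scale. That stands as to scope. A reader might infer that the whole patient-experience comparison is compromised, but PACIC-11 carries that domain and shows no screener. PROMIS, PHQ-4 and the EHR measures show none either.

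A reader might also infer that the plan drops screened-out patients, loses more of them in low practices, and leaves the screener unanalysed. The documents say none of this. The skip is inferred from the screener label and from the back-references in a column of example content. The equations are described as simplified, and PE is not defined at item level. The supportable statement is that the handling is not specified.

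The link to exposure rests on four of 40 checklist items, and practices are ranked on the total, which also counts activities far from the consultation, such as farmers markets. All sampled patients are established, with at least two primary care visits, which may narrow any gap in pass rates. Newly reached patients might rate staff as highly as others do. These points are fair, and they are why neither size nor sign can be asserted.

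Lastly, experience among patients who report a team is a legitimate conditional quantity. It is, provided it is labelled as such and shown beside the proportion who report one. The plan does not do this.

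**Conclusion.** The concern holds for the ACES care-team composite alone. As described, it can be scored only for patients who report a care team. Passing is a plausible consequence of high PA&E, and the Aim 1 and Aim 4 models do nothing about that selection. The illustrative -0.09 to -0.23 SD rests entirely on assumed pass rates of 70% v 50% and an assumed gap of 0.3 to 0.8 SD.

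Two stronger conclusions are tempting and not supported. One is that the bias runs against the study hypothesis: this needs both a higher pass rate in high practices and lower scores among the extra passers, and the documents show neither. The other is that the bias is as large as a minimally important difference: the 0.20 SD in the Measures section is for PROMIS physical functioning, and none is given for ACES.

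The point still goes beyond missing detail. If the screener answer is collected as described, analysing it over all respondents is a better method than comparing screened-in scores alone.

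**What to change.** In the analysis section:

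- State how screener-negative patients are handled at each wave, and how those who pass at one wave only enter the change analysis.
- At each wave, analyse the screener answer over all respondents as a patient-experience outcome, in a multilevel logistic model with the same terms as the PE model. Report pass rates by PA&E group and wave.
- Present the ACES composite beside that result, labelled as conditional on reporting a care team.
- Add one sensitivity analysis over all respondents that varies the assumed standing of screened-out patients over a plausible range. This could use a combined outcome (has a team and rates it highly), or shifts both below and above the screened-in mean. Do not use practice-mean imputation.
- Draw no care-team experience conclusion from the screened-in subset alone.

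The cost is some SAP wording, a few extra model runs on survey data already planned, and a less simple ACES summary. No new data collection is needed.
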